10.6 Continuation of treatment with investigational medicinal product

This is a phase 1 study in healthy subjects who will have no medical benefit from the treatment and thus there will be no treatment with C21 after end of study participation.

10.7 Treatment compliance

All IMP will be administered at the study site under medical supervision to ensure compliance. Dose information will be available in the eCRF.

10.8 Return and destruction of investigational medicinal products

Any unused IMP will be returned to the Sponsor or Sponsor delegate for destruction or destroyed at CTC after approval from Sponsor. All empty vials will be destroyed at the site upon confirmation from the Sponsor. The Monitor will perform final IMP accountability reconciliation at the study end to verify that all unused IMP will be adequately destroyed and documented.

11 STUDY ASSESSMENTS

The study assessments are described in the sections below and the timing of these assessments are detailed in the schedule of events (Section 8.1, Table 8.1-1).

11.1 Recording of data

The Principal Investigator will provide the Sponsor with all data produced from the scheduled study assessments during the study. He will ensure the accuracy, completeness, legibility, and timeliness of the data reported to Sponsor in the eCRF and in all required reports.

11.1.1 Informed consent

Signed informed consent must be obtained before any screening procedures are initiated. The informed consent procedure is further described in Section 14.3.

11.1.2 Eligibility criteria

Eligibility criteria should be checked during screening and relevant criteria confirmed before IMP administration on Day 1. The criteria are specified in Sections 9.4 and 9.5.

11.1.3 Demographic information

The following demographic data will be recorded: gender, age, dominant/non-dominant arm, ethnicity, and race.

11.1.4 Weight and height

Weight and height will be measured without shoes. BMI will be calculated, with one decimal, from the height and weight recorded.

11.1.5 Medical/surgical history

Medical/surgical history will be obtained by subject interview to verify that the eligibility criteria are met.

11.1.6 HIV and Hepatitis B/C

Subjects will be tested for HIV-1 and HIV-2 antibodies and HIV-1 p24 antigen, hepatitis B virus surface antigen and hepatitis C virus antibodies prior to inclusion into the study. Any positive result will exclude the subject from participating.

11.1.7 Alcohol test

An alcohol test will be performed at time points outlined in the schedule of events (Table 8.1-1).

11.1.8 Urine drug screen

Urine will be screened for drugs of abuse at time points outlined in the schedule of events (Table 8.1-1) using the Drug Screen Multi-12/15 (Nal von minden).

11.1.9 Physical examination

A complete physical examination will be performed at screening and will include assessments of the head, eyes, ears, nose, throat, skin, thyroid, neurological, lungs, cardiovascular, abdomen (liver and spleen), lymph nodes, and extremities.

Any abnormalities will be specified and documented as clinically significant or not clinically significant.

11.1.10 Prior and concomitant medications

Information on prior medications taken within 2 weeks prior to screening will be obtained by subject interview to verify that the eligibility criteria are met (see also Section 9.6.2).

Medications will be classified as prior if treatment is discontinued before the first IMP administration and as concomitant if ongoing at the time of the first IMP administration, stopped after the first IMP administration or started after the first IMP administration. To distinguish between prior and concomitant medications on Day 1 (*i.e.* the dosing day), the start time of any newly introduced medication or the stop time of any previously ongoing medication must be recorded in the eCRF.

Any use of prior/concomitant medications from screening (Visit 1) until the last end-of-study contact must be documented appropriately in the subject's eCRF. Relevant information (*i.e.* name of medication, dose, dose form, unit, route, frequency, start and stop dates, reason for use) must be recorded. All changes in medication should be noted in the eCRF.

11.1.11 Baseline symptoms

A baseline symptom is defined as a medical event that occurs between the subject's signing of the ICF until initiation of the study procedures on Day 1 (*i.e.* an event that occurs during the screening period). Such events are not AEs and will be recorded as baseline symptoms in the Medical History Log in the eCRF.

11.2 Efficacy assessments

11.2.1 Strain-gauge venous occlusion plethysmography

Measurements of FBF will be performed using a CE-marked automated strain-gauge venous occlusion plethysmography equipment providing on-line measurements; Bergenheim, Elektromedicin, Göteborg, Sweden.

The underlying principle of this method is that when the venous return from the forearm is briefly interrupted by inflating a cuff placed around the upper arm to well above venous pressure but below diastolic pressure, and arterial inflow continues unimpeded, the forearm swells at a rate proportional to the rate of arterial inflow. Changes in forearm volume result in a corresponding change in arm circumference and thus strain-gauge length, which can be detected as an alteration in electrical resistance of the gauge, and thus potential difference [16].

The subject will be placed resting in a comfortable supine position in a quiet room with normal room temperature (+20 °C to +25 °C) [14]. Both forearms must be positioned above the level of the heart to ensure adequate venous emptying during the period of deflation. This position will be achieved by resting the elbows on foam pads and supporting the hands with pillows. Cuffs will be placed on the widest part of both forearms and a smaller cuff will be placed around each wrist. The non-infused arm is used as a contemporaneous control to account for any minor changes in FBF affecting both arms, *e.g.* emotional stress or temperature changes.

A catheter will be inserted into the brachial artery of the nondominant arm according to standard hospital procedures. A standard arterial cannula will be used. The artery will be palpated at the elbow of the non-dominant arm. The skin will be cleaned with alcohol after which the artery is cannulated transcutaneously. A small infusion of saline will be connected to maintain the line opened.

After cannulation there will be a resting period of approximately 25 min. At the end of this resting period, baseline measurements of FBF will be performed.

The subject will receive ascending doses of C21 (3, 10, 30, 100 and 200 μ g/min) through local i.a. infusions for 5 min/dose with an infusion rate of 1 mL/min or 2 mL/min for the 200 μ g/min dose. The start -and stop times of the infusions will be recorded. Measurements of FBF will be performed in both arms simultaneously during the last 2 min of each infusion. The C21 doses will be separated by a wash-out period of at least 15 min. At the end of each wash-out period FBF will be measured and a baseline value for the next dose be recorded.

For each FBF measurement, an inflation pressure of 60 mmHg will be used for intervals of approximately 7 sec followed by approximately 8 sec of deflation. This cycle will be repeated approximately 8 times during the last 2 min of each infusion. The wrist cuff will be inflated to supra-systolic pressures within 30 sec before each measurement to exclude the hand circulation. Changes in forearm volume will be measured using strain-gauges placed around the widest part of the forearms. A measure of blood flow to that part of the forearm enclosed by the two cuffs is provided, expressed as mL per 100 mL of forearm volume per minute. Actual forearm volume can be estimated by calculation, assuming the forearm is a simple truncated cone, or by simple water displacement.

When the last C21 dose has been administered, the infusion will be discontinued and there will be a resting period of 20 min. At the end of this resting period, FBF will be measured and a baseline value for the first sodium nitroprusside dose will be recorded.

Infusions of sodium nitroprusside solution (Nipruss[®]) will be performed as a positive control, using the same methodology as described above. Ascending doses of 0.8, 1.6, and 3.2 μ g/min will be administered.

After removal of the arterial catheter a compression bandage will be applied to prevent bleeding.

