7.1.1 Primary endpoint

The primary endpoint is percent change from baseline in FBF, in response to increasing i.a. doses of C21.

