8 STUDY DESIGN

8.1 Overall study design and schedule of events

This is a phase 1, open-label, single-centre study investigating the effects of i.a. infusions of the AT_2R agonist C21 on FBF in 5 healthy male subjects, by use of strain-gauge venous occlusion plethysmography.

Consenting subjects will be screened for eligibility according to study-specific eligibility criteria (see Sections 9.4 and 9.5) within 30 days prior to IMP administration (Visit 1; screening).

Eligible subjects will be scheduled for a treatment visit (Visit 2; Day 1). Relevant inclusion/exclusion criteria will be confirmed and a standardised meal (breakfast or lunch depending on the time of the day) will be served 60 minutes (min) prior to the first FBF measurement.

Measurements of FBF will be performed using a Conformité Européenne (CE)-marked automated strain-gauge venous occlusion plethysmography equipment providing on-line measurements, following a pre-specified procedure (see Section 11.2.1).

The subjects will be placed resting in a comfortable supine position in a quiet room with normal room temperature (+20 to +25° C) [14] with the forearms positioned above the level of the heart. Cuffs will be placed on the widest part of both forearms and a smaller cuff will be placed around each wrist. The non-infused arm is used as a contemporaneous control to account for any minor changes in FBF affecting both arms, *e.g.* emotional stress or temperature changes.

A catheter will be inserted into the brachial artery of the nondominant arm following standard hospital procedures (see Section 11.2.1) and a resting period of approximately 25 min will follow. At the end of this resting period, baseline measurements of FBF will be performed.

Ascending doses of C21 (3, 10, 30 100 and 200 μ g/min) will be administered through local i.a. infusions for 5 min/dose with an infusion rate of 1 mL/min or 2 mL/min for the 200 μ g/min dose. Measurements of FBF will be performed in both arms simultaneously during the last 2 min of each infusion/dose. The C21 doses will be separated by a wash-out period of at least 15 min. At the end of each wash-out period FBF will be measured and a baseline value for the next dose will be recorded. The Investigator will assess any emerging AEs by subject interview between each dose before deciding to proceed to the next dose level.

A flow-chart of the C21 dosing and FBF measurement schedule is presented in Figure 8.1-1.

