8.2 Rationale for study design

This study evaluates for the first time the dose-response related vasodilative effects of C21.

Suggested dose escalation design and i.a. infusion has been widely used in the FBF design for the past 80 years contributing to exploring human vascular physiology in vivo [11] and is considered as a golden standard in the assessment of vascular function.

Strain-gauge venous occlusion plethysmography will be use as a method for assessment of the primary endpoint (see Section 6.4).

The study design involves careful monitoring of the subject's well-being. Furthermore, by infusing IMP locally, drug-induced changes in blood pressure and cardiovascular reflexes can be minimised.

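### The cuff-placement sentence for forearm blood flow contradicts the protocol's own measuring principle and gives the cuffs the strain-gauge site; it is wrong as written in three places

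*Combined protocol and SAP*

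**What the plan says.** Section 11.2.1 opens with the principle of the method. Venous return is briefly interrupted "by inflating a cuff placed around the upper arm to well above venous pressure but below diastolic pressure", arterial inflow continues, and the rate of forearm swelling reflects that inflow.

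The next paragraph of the same section gives the set-up: "Cuffs will be placed on the widest part of both forearms and a smaller cuff will be placed around each wrist". The identical sentence appears in the synopsis (Methodology) and in Section 8.1.

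Later in Section 11.2.1 the gauge position is given: "Changes in forearm volume will be measured using strain-gauges placed around the widest part of the forearms". The measured quantity follows: "A measure of blood flow to that part of the forearm enclosed by the two cuffs is provided". Each measurement uses an inflation pressure of 60 mmHg for about 7 seconds, then about 8 seconds of deflation, repeated about 8 times. The wrist cuff is taken above systolic pressure to exclude the hand.

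Section 8.1 refers the reader to Section 11.2.1 for the pre-specified procedure. Section 7.1.1 states what rests on it: "The primary endpoint is percent change from baseline in FBF, in response to increasing i.a. doses of C21".

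**The concern.** The only sentence that tells staff where to put the cuffs names a different site from the sentence that explains why the method works. It also names the site assigned to the strain gauge. A cuff inflated over the gauge compresses the tissue whose free swelling the gauge is meant to record.

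FBF is the only efficacy measurement. It feeds the percent change for C21 (Section 17.5.1), the dose-response model (Section 17.5.2) and the nitroprusside control (Section 17.5.3). Two features of the design would not repair a wrong set-up. The instruction covers both forearms, so the non-infused arm would be set up the same way. Each baseline would come from the same set-up as the infusion value compared with it.

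**Working it through.** No sample-size or effect figure is involved, so the check is a comparison of every statement on cuff or gauge position.

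| Item | Position given | Where |
|---|---|---|
| Cuff that interrupts venous return | Upper arm | 11.2.1, principle paragraph |
| Larger cuffs, set-up instruction | Widest part of both forearms | Synopsis, 8.1, 11.2.1 |
| Smaller cuffs | Wrists | Synopsis, 8.1, 11.2.1 |
| Strain gauges | Widest part of the forearms | 11.2.1, measurement paragraph |
| Segment measured | Forearm between the two cuffs | 11.2.1, measurement paragraph |

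Three readings are possible.

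1. *Literal.* The proximal cuff is at the widest part of the forearm and the distal cuff is at the wrist. The gauge shares the proximal cuff's site, so it is at the edge of the measured segment or under the cuff, not within the segment. The 60 mmHg sentence does not name its cuff. Since the wrist cuff goes above systolic pressure, 60 mmHg must apply to the other one, which on this reading is the cuff at the gauge. This fails both the stated principle and the stated measured segment.
2. *An upper-arm cuff in addition to the forearm cuff.* That makes three cuffs per arm, but the measurement paragraph counts two. The text does not support it.
3. *The word for cuffs is a slip for strain gauges.* The gauge and wrist positions then agree with the rest of the section. But no set-up sentence now says where the occluding cuff goes; only the explanation of the principle does.

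The text needs correcting under all three. Only a cuff on the upper arm paired with the wrist cuff satisfies the principle, the gauge site and the measured segment together.

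The sentence appears word for word in three places, so it is not an artefact of reading the PDF. I found no other text that corrects it.

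The number of recordings that the sentence governs, taking one recording per infusion and one per baseline:

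- Infused arm, primary endpoint: 5 C21 infusions × 2 (infusion and its baseline) × 5 subjects = 50.
- Infused arm, with nitroprusside: (5 + 3) × 2 × 5 = 80.
- Both arms: 80 × 2 = 160. This assumes that both arms are recorded at every baseline. Section 11.2.1 says so only for the infusion measurements.

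These counts show reach. They are not effect sizes.

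**The case against.** The strongest reply is that the intended set-up can be recovered from Section 11.2.1. The one sentence that names the occluding cuff puts it on the upper arm, and the gauge sentence closely resembles the cuff sentence, which points to the gauge site having been written in for the cuff site. The study runs at one centre with CE-marked automated equipment, and staff are trained in study-specific procedures before enrolment (Section 15.1). Literal execution is therefore less likely. All of this stands.

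It does not remove the defect. Section 8.1 makes Section 11.2.1 the procedure, training covers the protocol's requirements (Section 15.1), and the Monitor confirms adherence to it (Section 15.2). Staff who follow the principle depart from an instruction given three times; staff who follow the instruction depart from the principle.

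A reader might infer that sessions set up differently would not be comparable. The documents do not support that as a general claim. Each subject has one treatment visit, with a baseline for each dose level. If a set-up multiplied every flow value in a session by a constant k, percent change would be unaffected: (kF₁ − kF₀)/(kF₀) = (F₁ − F₀)/F₀. The dose-response model uses log maximum FBF without baseline adjustment, but ln(kF) = ln k + ln F, and the subject effect takes up ln k. This protection covers only a constant proportional error. It would not rescue a recording made with the gauge under an inflated cuff.

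**Conclusion.** The point holds as an internal inconsistency in the procedure for the primary measurement: wrong as written. It is not a questionable design choice, since nothing in the protocol argues for occlusion at the forearm.

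The consequence is conditional. If the sentence were followed literally, the set-up would not give a valid FBF measurement for the primary endpoint, the dose-response curve or the positive control. A reader might go further and infer that the study's FBF values are invalid. The documents do not support that: they do not show that the measurement would be executed this way, and a drafting slip is the likelier explanation. They also give no basis for the probability of a wrong set-up or the size of the resulting error.

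Correction is still needed before the text is relied on, because the sentence governs the only efficacy measurement and the protocol alone would not tell a later reader which set-up produced the data.

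**What to change.** Replace the cuff sentence in the synopsis, Section 8.1 and Section 11.2.1 with one that matches the protocol's own principle and gauge position: occluding cuffs around both upper arms, strain gauges around the widest part of both forearms, and small cuffs around the wrists. Use the same wording in all three places.

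The cost is a wording change in three places, documented as a protocol amendment under Section 14.6. It adds no procedure, staff, subjects or visit time, and it leaves the analysis in Section 17.5 unchanged.

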Figure 8.1-1 Dosing and measurement flow-chart for C21 infusions

When the last C21 dose has been administered there will be a resting period of 20 min. At the end of this resting period, FBF will be measured and a baseline value for the first sodium nitroprusside dose will be recorded.

CONFIDENTIAL

Infusions of sodium nitroprusside solution (Nipruss[®]) will be performed as a positive control, using the same methodology as described above. Ascending doses of 0.8, 1.6, and 3.2 μ g/min will be administered. A flow-chart of the Nipruss[®] dosing and FBF measurement schedule is presented in Figure 8.1-2.

Safety assessments (blood pressure, pulse, ECG, and safety laboratory parameters) will be performed prior to first dose of IMP and before the subject leaves the clinic. Any occurrence of AEs during the procedure will be recorded.

After removal of the arterial catheter a compression bandage will be applied to prevent bleeding. Written instructions regarding how to handle the bandage, how to manage symptoms and when and how to contact the Investigator if necessary, will be provided to the subject before leaving the clinic.

A follow-up phone call (end-of-study) will be performed 7 to 10 days after the treatment visit (Visit 2).

The schedule of events is shown in Table 8.1-1. Study assessments are described in Section 11.

Table 8.1-1 Schedule of events

		Screening	Treatment	End-of- study
Visit/contact	Refer to CSP section:	Visit 1	Visit 2	Follow-up call
Assessment		Day -30 to Day -1	Day 1	Day 8 to Day 11
Informed consent	14.3	X		
Inclusion/exclusion criteria	9.4, 9.5	X	\mathbf{X}^{1}	
Demographics	11.1.3	X		
Weight, height, BMI	11.1.4	X		
Medical/surgical history	11.1.5	X		
HIV, hepatitis B and C	11.1.6	X		
Alcohol test	11.1.7	X	Х	
Urine drug screen	11.1.8	X	Х	
Physical examination	11.1.9	X		
Clinical laboratory profile ²	11.3.4	X	X ³	
Vital signs (blood pressure and pulse)	11.3.2	X	X^3	
12-lead safety ECG	11.3.3	X	X ³	
Standardised breakfast/lunch	9.6.1		X^4	
IMP administration	10.5		Х	
FBF measurements (plethysmography)	11.2.1		X^5	
Baseline symptoms	11.1.11	X	X ⁶	
Adverse events	11.3.1		X^7	X
Prior and concomitant medications	11.1.10	X	Х	X

1. Confirmation of relevant inclusion/exclusion criteria.

2. Clinical chemistry, haematology and coagulation.

3. Before first IMP administration and before leaving the clinic.

4. Served 60 min prior to first FBF measurement.

5. For detailed procedures and timepoints, see Section 11.2.1.

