9.5 Exclusion criteria

Subjects must not enter the study if any of the following exclusion criteria are fulfilled:

- 1. History of any clinically significant disease or disorder which, in the opinion of the Investigator, may either put the subject at risk because of participation in the study, or influence the results or the subject's ability to participate in the study.
- 2. History of thrombotic disease, vascular disorder, or severe bleeding disease.
- 3. Poor brachial artery access.
- 4. Any clinically significant illness, medical/surgical procedure, or trauma within 4 weeks of Day 1 (Visit 2).
- 5. Malignancy within the past 5 years with the exception of basal cell or squamous epithelial carcinomas of the skin that have been resected with no evidence of metastatic disease for 3 years.
- 6. Any planned major surgery within the duration of the study.
- 7. Any positive result on screening for serum hepatitis B surface antigen, hepatitis C antibody and human immunodeficiency virus (HIV).
- 8. After 10 min supine rest at the time of screening, any vital signs values outside the following ranges:
 - Systolic blood pressure <100 or >140 mmHg, or
 - Diastolic blood pressure <50 or >90 mmHg, or
 - Pulse <45 or >90 beats per minute (bpm)
- 9. Prolonged QTcF (>450 ms), cardiac arrhythmias or any clinically significant abnormalities in the resting ECG at the time of screening, as judged by the Investigator.
- 10. History of severe allergy/hypersensitivity or ongoing allergy/hypersensitivity, as judged by the Investigator, or history of hypersensitivity to drugs with a similar chemical structure or class to the IMPs, including any of the excipients of the IMPs.
- 11. Regular use of any prescribed or non-prescribed medication including antacids, analgesics, herbal remedies, vitamins, and minerals within 2 weeks prior to Day 1 (Visit 2), at the discretion of the Investigator.
- 12. Regular use of non-steroidal anti-inflammatory drugs (NSAIDs) or acetylsalicylic acid (ASA) within 2 weeks prior to Day 1 (Visit 2).
- 13. Vaccination within 1 week prior to dosing or plans to receive any vaccine during the study conduct.
- 14. Planned treatment or treatment with another investigational drug within 3 months prior to Day 1 (Visit 2). Subjects consented and screened but not dosed in previous phase 1 studies are not excluded.

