11.3.2 Vital signs

Systolic and diastolic blood pressure and pulse will be measured in supine position after 10 min of rest at time-points specified in Table 8.1-1.

Any vital signs outside the normal ranges will be judged as not clinically significant or clinically significant by the Investigator. The assessment will be recorded in the eCRF. Abnormal post-dose values judged as clinically significant will be reported as AEs.

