17.6.2 Vital signs

Vital signs (systolic/diastolic blood pressure and pulse) will be summarised using descriptive statistics. Data will be presented with absolute change from baseline.

Individual data will be listed by subject.

17.6.3 12-lead ECG

All ECGs will be categorised as *normal, abnormal, not clinically significant*, or *abnormal, clinically significant* (as judged by the Investigator) and summarised using descriptive statistics.

Individual data will be listed by subject.

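### The fixed 60 mmHg occluding cuff breaks the method's own below-diastolic condition for subjects admitted with a diastolic pressure of 50 to 60 mmHg

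*Combined protocol and SAP*

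**What the plan says.** Three statements in the protocol bear on this.

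- **Principle of the method (11.2.1).** Venous return is interrupted by "inflating a cuff placed around the upper arm to well above venous pressure but below diastolic pressure, and arterial inflow continues unimpeded". Under that condition the rate of forearm swelling represents arterial inflow.
- **Operating instruction (11.2.1).** "For each FBF measurement, an inflation pressure of 60 mmHg will be used for intervals of approximately 7 sec". The wrist cuff is described separately and goes to supra-systolic pressure, so the 60 mmHg must refer to the venous occluding cuff.
- **Eligibility (9.5, criterion 8).** Subjects are excluded for "Diastolic blood pressure <50 or >90 mmHg", assessed as follows: "After 10 min supine rest at the time of screening, any vital signs values outside the following ranges". Values from 50 to 90 mmHg are therefore admitted. Section 8.1 places screening "within 30 days prior to IMP administration (Visit 1; screening").

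On Day 1, blood pressure is scheduled (Table 8.1-1, footnote 3) "Before first IMP administration and before leaving the clinic". Section 11.3.2 adds that "Systolic and diastolic blood pressure and pulse will be measured in supine position after 10 min of rest", and section 17.6.2 that "Individual data will be listed by subject". Nothing links these readings to the cuff pressure, and nothing says how flow data are handled if diastolic pressure is at or below 60 mmHg.

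**The concern.** The plan gives a condition under which its measurement is valid, then fixes a setting that does not meet it for some subjects it admits. If the cuff is at or above diastolic pressure, inflow may be impeded and the reading may no longer represent flow.

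Forearm blood flow (FBF) is the only efficacy measurement. It carries the primary endpoint, the C21 dose-response curve and the positive control. With 5 evaluable subjects, one affected subject is 20% of the data. The eligibility limit applies only at screening. The Day 1 listings would show the margin to 60 mmHg at the two ends of the session but not during it.

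**Working it through.** The plan has no figure of its own to reproduce here: section 17.2 states that no formal sample size calculation was made. The check has four steps.

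**1. Does the condition hold over the admitted range?** The inputs are cuff = 60 mmHg (11.2.1) and admitted diastolic pressure = 50 to 90 mmHg inclusive (9.5). The condition is cuff < diastolic. It fails at every whole value from 50 to 60: at 60 the two are equal, and at 50 the cuff is 10 mmHg higher. That is 11 of 41 admissible whole-mmHg values, which is a share of the permitted range and not of subjects.

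**2. How likely is an affected subject?** The documents give no diastolic distribution, so one is assumed: normal with mean m and SD s, truncated to 50-90 mmHg.

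p = P(50 ≤ DBP ≤ c) / P(50 ≤ DBP ≤ 90); chance of at least 1 of 5 = 1 − (1 − p)^5.

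| Assumed m / s | c = 55: chance | c = 60: chance |
|---|---|---|
| 70 / 8 | 0.117 (p = 0.0245) | 0.412 (p = 0.101) |
| 75 / 7 | 0.010 | 0.078 |
| 65 / 9 | 0.376 | 0.769 |
| 78 / 6 | 0.0003 | 0.007 |
| 65 / 10 | 0.407 | 0.779 |

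The c = 60 column matches the stated conflict. The c = 55 column leaves out men close to the cuff pressure.

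**3. What would it do to the primary endpoint?** Suppose an affected subject loses a fraction of the true flow reading. Then

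observed change = (1 + true change) × (1 − loss at dose) / (1 − loss at baseline) − 1.

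With a true change of +100% and assumed losses:

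| Loss at baseline / dose | Observed change | Shift in subject | Shift in mean of 5 |
|---|---|---|---|
| 0.10 / 0.10 | 100.0% | 0 | 0 |
| 0.05 / 0.06 | 97.9% | −2.1 points | −0.42 |
| 0.10 / 0.11 | 97.8% | −2.2 points | −0.44 |
| 0.10 / 0.09 | 102.2% | +2.2 points | +0.44 |

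A stable proportional loss therefore cancels. Only a change in loss between a baseline and its dose reading matters. Those readings are minutes apart, because the dose reading falls in the last 2 minutes of the 5-minute infusion that follows its baseline. For scale, an assumed between-subject SD of 20 to 50 points gives a standard error of 20/√5 = 8.9 to 50/√5 = 22.4 points.

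**4. What would it do to the dose-response model (17.5.2)?** With 1 of 5 subjects affected and complete data:

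- Pairwise comparison, loss 0.05 at one dose and 0.06 at another: exp(ln(0.94/0.95)/5) − 1 = −0.21% on the LSMeans ratio. This needs a change across the C21 session, which lasts at least 5×5 + 4×15 = 85 minutes.
- Plotted level, stable loss L: exp(ln(1 − L)/5) − 1 = −1.0% (L = 0.05), −2.1% (0.10) and −4.4% (0.20). Every dose shifts equally, so the curve's shape and the pairwise differences are unchanged.

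**The case against.** The case against giving this much weight is fair on several counts.

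- **The below-diastolic wording explains the principle and is not a numbered requirement.** True. But it stands in the efficacy-assessment section and is the protocol's own reason for reading the signal as flow.
- **The cuff at 60 mmHg is not named.** Reading it as the venous cuff is an inference, though a safe one given the wrist cuff's supra-systolic pressure. Cuff location is also unclear: section 11.2.1 puts it on the upper arm in the principle and on the widest part of the forearms in the set-up.
- **Partial safeguards exist.** Inclusion criterion 5 requires vital signs that the Investigator judges normal, and relevant criteria are confirmed on Day 1 (8.1, 11.1.2). Neither sets a numeric diastolic limit that closes the gap.
- **The non-infused arm is a simultaneous control.** It could help to examine drift, but sections 17.5.1 and 17.5.2 do not say how it enters the analysis.
- **The effect is negligible and the figures rest on assumptions.** A shift of about 0.4 points is some 2% to 5% of one assumed standard error (0.42/22.4 to 0.44/8.9). The chance of an affected subject spans a range too wide to inform much. This stands, and it limits the finding to a minor one.
- **Neither remedy detects drift within the session, which is what could distort the primary endpoint.** True. A stated margin only makes crossing less likely.

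None of this removes the conflict between the passages.

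**Conclusion.** The concern holds, as a minor internal inconsistency. Taken together, sections 9.5 and 11.2.1 admit subjects for whom the fixed cuff pressure does not satisfy the method's stated condition, and no other section resolves it.

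Its size is small and possibly nil, since 0 of 5 subjects may be affected. The primary endpoint is distorted only if the error changes between a baseline and its dose reading. Dose comparisons are distorted only if it changes across the session. The plotted LSMeans levels shift only if an affected subject is enrolled. The direction of any distortion in percent change is not known, because the loss could rise or fall. The downward level shift follows only from assuming a loss.

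The contradiction itself needs no assumption. The probabilities, loss fractions, true response and between-subject SD are all assumed, because the documents give none of them. Confidence is medium.

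**What to change.** Reconcile criterion 8 in section 9.5 with the two statements in section 11.2.1, in one of two ways.

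1. **Tie the cuff to the subject.** State in 11.2.1 that the occluding-cuff pressure is set below the subject's own Day 1 supine diastolic pressure by a margin the sponsor specifies, remains well above venous pressure, is held constant through the session, and is recorded with the FBF data. The diastolic reading must precede the first baseline FBF reading.
2. **Make the limits agree.** Bring the diastolic eligibility limit and the fixed cuff pressure into line, and say whether the limit is rechecked on Day 1.

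Either way, 11.2.1 should name the cuff concerned and its position.

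The cost is one or two sentences. The Day 1 supine blood pressure is already scheduled, so only its timing relative to the first baseline FBF reading has to be stated; option 1 also adds one recorded value. The downside of option 1 is that cuff pressure may differ between subjects. The downside of option 2 is a slightly narrower eligible pool if the limit is moved.
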